9.3 Dose-response analyses for continuous data

Changes from baseline to Week 8 for other continuous OBPM endpoints will be analyzed using the general MCP-Mod approach which consists of two steps.

First an ANCOVA model is fitted with a factor for treatment group and a covariate for the baseline value. The SAS statements (using mock variable names and values) for this model are:

```
ods output lsmmeans=lsm * export data set lsm as xpt file;
proc mixed data=dset;
  class treat;
  model outcome=treat base;
  lsmmeans treat/ cov;
  where week=8 and treat in (0,1,2,3,4);
run;
```

Here, treat=0, 1, 2, 3, and 4 for placebo, 5 mg, 10 mg, 25 mg and 50 mg of ACT-132577, respectively. Note that the active comparator (treat=5) is excluded from this analysis.

Then the LSMeans from this model will be analyzed using the general MCP-Mod approach. The R statements for this analysis are (Delta=3 for DBP; Delta=5 for SBP):

```
# read data frame lsm from xpt file
est <- lsm$ESTIMATE # LSMeans
C <- lsm[,c("COV1","COV2","COV3","COV4","COV5")] # covariance matrix
doses <- c(0,5,10,25,50)
MMfit <- MCPMod(type="general", dose=doses, resp=est, S=as.matrix(C),
models=candMod, Delta=3, alpha=0.05)
```

Repeated measurements (e.g., changes from baseline to Weeks 2, 4 and 8) will be analyzed in two ways: focusing on the last time point (e.g., Week 8 and using Week 2 and Week 4 only to predict missing data, if needed) and estimating the average effect over time. In both cases the general MCP-Mod approach was used.

Last time point. First a mixed model is fitted with factors for treatment group, time and treatment by time interaction and covariates for the baseline value and the interaction between baseline and time. An unstructured covariance matrix will be used to account for the correlation between repeated measurements from the same subject. The SAS statements for this model are:

```
ods output lsmmeans=lsm1 (where=(week=8)); * export data set lsm1 as xpt file;
proc mixed data=dset noclprint=6;
  class treat week subjid;
  model outcome=treat week treat*week base base*week;
  repeated week/ subject=subjid type=un;
  lsmmeans treat*week/ cov;
  where treat in (0,1,2,3,4);
run;
```

The LSMeans at Week 8 will then be analyzed using the general MCP-Mod approach. The R statements for this analysis are the same as above, except for:

```
C <- lsm[,c("COV3","COV6","COV9","COV12","COV15")] # covariance matrix
```

Average over time. First the same mixed model is fitted, but without the treatment by time interaction. The SAS statements for this model are:

```
ods output lsmeans=lsn2; * export data set lsn2 as xpt file;
proc mixed data=dset noclprint=6;
  class treat week subjid;
  model outcome=treat week base base*week;
  repeated week/ subject=subjid type=un;
  lsmeans treat/ cov;
  where treat in (0,1,2,3,4);
run;
```

Then the LSMeans (averages over time) will be analyzed using the same R statements as above with:

```
C <- lsm[,c("COV1","COV2","COV3","COV4","COV5")] # covariance matrix
```

9.4 Dose-response analyses for binary data

Binary outcomes include the control and response status for DBP (or SBP) at a fixed time point and will also be analyzed using the general MCP-Mod approach. First a logistic regression model is fitted with a factor for treatment group and a covariate for the baseline value of DBP (or SBP). The SAS statements (using mock variable names and values) for this model are:

```
ods output lsmeans=lsn * export data set lsn as xpt file;
proc logistic data=dset descending;
  class treat/param=glm;
  model resp=treat base;
  lsmeans trt01pn/ ilink cov;
  where week=8 and treat in (0,1,2,3,4);
run;
```

Then the estimated differences vs placebo (in data set diff) will be analyzed using the general MCP-Mod approach [Pinheiro 2014].

```
# read data frame lsm from xpt file
est <- lsm$MU #LSMeans
C <- diag(lsm$STDERRMU^2)
candMod <- Mods(linear = NULL, linlog = NULL, quadratic = -0.005, emax = 50,
```

```
sigEmax = c(50, 0.5), logistic = c(50, 50), doses = doses,  
direction="increasing")  
MMfit <- MCPMod(type="general", dose=doses, resp=est, S=as.matrix(C),  
models=candMod, Delta=0.1, alpha=0.05)
```

Since control and response statuses are not expected to change much over time (i.e., from Week 2 to 8) a repeated measures analysis of these binary endpoints was omitted.

10 STATISTICAL ANALYSES

10.1 Overall testing strategy

All statistical testing will be performed at a two-sided significance level of 0.05 using 95% confidence intervals (CIs).

In the main analysis of the primary endpoint in the PPS the type I error is controlled by the MCT part of the MCP-Mod methodology. The primary objective of the trial will be evaluated based on this analysis.

The type I error of the MCP-Mod analysis in the FAS is similarly protected. In the other supportive analysis of the primary endpoint Dunnett's test will be used to correct for testing multiple doses vs placebo. The alpha is formally controlled only for the main analysis; all other analyses are considered exploratory.

In all analyses of secondary and other efficacy variables, no correction will be made for multiple testing.

10.2 General rules for data presentations

This section describes the general rules applied for all data displays.

SAS version 9.3 is used for the statistical analyses except for the primary endpoint (dose-response analysis) that is analyzed by means of the R package.

Unless otherwise specified in this document:

- All listings are sorted by randomized treatment, subject number and, when appropriate, by visit / date of assessment. If a listing includes non-randomized subjects, these will appear after the randomized subjects. All data collected are displayed, including unscheduled visits (if any).
- In summary tables and graphical representations, subjects are grouped by randomized treatment group, except for the SAF for which the actual treatment is used.
- In summary tables based on the RND, FAS, PPS and SAF, the order of the treatment groups is: placebo, ACT-132577 5 mg, ACT-132577 10 mg, ACT-132577 25 mg, ACT-132577 50 mg and Lisinpril 20 mg, followed by Total (if required). In summary tables based on the RIS or SCR, only a total column will be given.

- The absolute change from baseline to Visit X is defined as the difference between the post-baseline Visit X value and the baseline value.
- In order to analyze the data at the relevant planned (scheduled) visits, all recorded assessments for each subject up to the Week 10 visit are reassigned to the most appropriate visit according to the time window for that visit. The windows are consecutive (i.e., there are no gaps) and are based on the study day corresponding to the date of assessment. Any unscheduled visit is also mapped to a time window. Details of the visit mapping are given in Section 11.1.
- According to section 11.3.2.2 of the protocol, imputation rules for missing data are defined for the evaluation of efficacy endpoints at Week 8. Subjects without a value in the defined Week 8 time window are included in the analysis according to the rules highlighted in Section 9.

10.3 Display of subject disposition, protocol deviations and analysis sets

10.3.1 Subject disposition

Summary tables are provided, on the SCR, RIS and RND sets [see Section 7 for terminology], by treatment group (where applicable) and overall, to display the following information:

- Disposition of subjects (screened, entered in run-in, randomized, treated i.e., who received at least one dose of study treatment, who completed treatment - see Section 5.3.3 for definition, who completed study - see Section 5.4 for details). This summary table is also provided by site.
- Reasons for screening failures [see definition in Section 5.1, overall only].
- Reasons for run-in failures [see definition in Section 5.1, overall only].

Percentages are calculated based on screened subjects [see definition in Section 5.1] or run-in subjects where appropriate. A listing of screening failures is provided for the SCR and a listing of run-in failures for the RIS. Randomization scheme and codes and code break or subject unblinding (if any) are provided in separate listings on the RND set.

10.3.2 Protocol deviations

All important PDs (as defined by the PD list) will be summarized on the FAS by categories, displaying counts and percentages of subjects with at least a PD, by treatment group and overall. This summary table is sorted, within each PD temporal category, by overall frequency, in descending order; if a tie occurs, the tied characteristics will be sorted alphabetically.

All reported PDs will be reported in a subject listing on the SCR set. Important PDs will be flagged accordingly.

10.3.3 Analysis sets

A summary table is provided on the RND set to display the composition of FAS, PPS and SAF analysis sets, by treatment group and overall. A listing of subject participation in the different analysis sets is also provided.

A separate summary table is provided on the RND set to display the reasons for exclusion from the above analysis sets, by treatment group and overall. In addition, the same table is provided by site.

10.4 Analyses of subject characteristics

10.4.1 Demographics

All data [see definition in Section 5.2.1] will be reported in a subject listing based on the RND. The listing will include the other baseline characteristics defined in Section 5.2.3.

Demographic characteristics will be summarized using descriptive statistics by treatment group as well as overall for the FAS and PPS.

Note that age will be summarized as a continuous variable as well as a categorical variable (< 65 , ≥ 65 years). Age as per EudraCT categories (18–64, 65–84, ≥ 85 years) will be tabulated separately based on the FAS.

10.4.2 Baseline disease characteristics

All data [see definition in Section 5.2.2] will be reported in a subject listing based on the SCR. Baseline disease characteristics will be summarized by treatment group as well as overall for the FAS and PPS.

10.4.3 Other baseline characteristics.

Other baseline disease characteristics [see definition in Section 5.2.3] will be summarized by treatment group and overall using descriptive statistics for the FAS and PPS.

10.4.4 Medical history

All previous or ongoing diseases / diagnoses [see definition in Section 5.2.4] will be reported in a subject listing. Ongoing diseases / diagnoses will be flagged accordingly. Previous and ongoing diseases / diagnoses will be summarized in separate tables. This will be done for the FAS and PPS.

Previous or ongoing diseases / diagnoses will be summarized by treatment group and overall, together displaying counts and percentages of subjects having experienced at least one disease. Counts and percentages of subjects having experienced at least one disease are presented by system organ class (SOC) and individual preferred term within each SOC. The summary table is presented in descending order according to the

incidence in the highest-dose of active test treatment (e.g., SOC and individual preferred term within each SOC with the highest number of occurrences appears first). Equal frequency of different SOC / individual preferred terms is sorted in alphabetical order of the SOC / individual preferred term.

The counting of the diseases is handled as follows:

- Subjects with two or more occurrences of the same disease (as qualified by the same preferred term[s]) are counted only once.
- In the event that the reported disease is assigned to several preferred terms, subjects are counted for each individual preferred term.

10.4.5 Previous and concomitant therapies

For study reporting purposes, all previous and/or concomitant therapies will be reported in a subject listing.

Counts and percentages of subjects having taken at least one previous, study concomitant and double-blind treatment concomitant therapy [see definition in Section 5.2.5] are presented by treatment group, by ATC class and individual preferred term within each ATC class, separately.

The summary tables are presented in descending order according to the incidence in the highest-dose of active test treatment (e.g., ATC and individual preferred term within each ATC with the highest number of occurrences appear first). Equal frequency of different ATC / individual preferred terms is sorted in alphabetical order of the ATC / individual preferred term.

The counting of the therapies is handled as follows:

- Subjects who took the same therapy more than once (as qualified by the same preferred term[s]) are counted only once.
- In the event of the reported medication being assigned to several preferred terms, subjects are counted for each individual preferred term.

For each preferred term the class are allocated using the 3 digits of the ATC code.

Specific previous and concomitant therapies will be displayed separately as described above.

10.4.6 Other subject characteristics

Not applicable.

10.5 Analysis of study treatment duration and compliance

10.5.1 Study treatment duration

The duration of double-blind study treatment [see definition in Section 5.3.1] will be summarized on the PPS and SAF using descriptive statistics. Additionally, double-blind study treatment will be summarized as categorical variable, presenting the cumulative distribution by class interval categorized as 0–2, > 2–4, > 4–8 and > 8 weeks and displaying counts and percentages of subjects in each class interval.

In addition, run-in study treatment duration will be summarized for the RIS.

10.5.2 Compliance with study treatment

Double-blind treatment compliance [see definition in Section 5.3.2] will be summarized on the FAS and PPS displaying counts and percentages of subjects with compliance categorized as: < 80%, 80–120%, and > 120%. Run-in treatment compliance will be summarized similarly for the RIS.

10.5.3 Study treatment discontinuation

A summary table is provided for the SAF to display counts and percentages of subjects who prematurely discontinued double-blind study treatment, as well as the associated reasons [see definition in Section 5.3.3], by treatment group and overall.

Note that premature double-blind study treatment discontinuation does not necessarily imply study withdrawal.

In addition, premature run-in treatment discontinuation will be summarized for the RIS.

10.5.4 Study treatment adjustments or interruptions

The number and percentage of subjects with DB study treatment interruptions will be provided for the SAF. The associated reasons will be summarized similarly.

10.5.5 Study withdrawal

A summary table is provided for the RND to display counts and percentages of subjects who prematurely discontinued the study after randomization, as well as the associated reasons by treatment group and overall. A listing of discontinued subjects is provided on the RND set. A similar table and listing based on the RIS will be provided for premature study discontinuation during run-in.

10.6 Analysis of the primary efficacy variable(s)

The primary efficacy variable (change from baseline to Week 8 of DB treatment in mean trough SiDBP, measured by OBPM) will be analyzed in the PPS and the FAS. The PPS analysis is the primary analysis, the analysis in the FAS is supportive.

The primary efficacy variable will be summarized by treatment group using descriptive statistics for the PPS and FAS.

10.6.1 Hypothesis and statistical model

The null hypothesis associated with the primary endpoint is that there is no dose-response relationship.

$$H_0: \mu_0 = \mu_1 = \mu_2 = \mu_3 = \mu_4$$

Here, μ_i denotes the mean change from baseline to Week 8 in mean trough SiDBP (μ) for ACT-132577 dose (i) (where $i = 0$ corresponds to placebo). A value of $\mu_i < 0$ corresponds to a decrease in SiDBP.

The alternative hypothesis is that there is a monotonic dose-response for the primary endpoint.

$$H_1: \mu_0 \geq \mu_1 \geq \mu_2 \geq \mu_3 \geq \mu_4 \text{ and } \mu_i > \mu_j \text{ for at least one } i > j \text{ or} \\ \mu_0 \leq \mu_1 \leq \mu_2 \leq \mu_3 \leq \mu_4 \text{ and } \mu_i < \mu_j \text{ for at least one } i > j$$

Note that larger values of μ_i – corresponding to less decrease (or more increase) from baseline to Week 8 in mean trough SiDBP with increasing dose of ACT-132577 – are less favorable. The first part of the alternative hypothesis corresponds to ACT-132577 being superior to placebo, whereas the second part corresponds to ACT-132577 being worse than placebo.

10.6.2 Handling of missing data

In the PPS there will be no missing data from the primary endpoint given the definition of PPS. For the handling of missing data in the FAS, refer to Section 9.1.

[figure not shown]
10.6.3 Main analysis

The change from baseline to Week 8 of DB treatment period (Period II) in mean trough SiDBP will be analyzed using the MCP-Mod approach [Bretz 2005, Pinheiro 2006] described in Section 9.1.

A placebo-corrected mean reduction from baseline of at least 4 mmHg is considered clinically relevant.

Some examples of E_{\max} dose-response relationships are given in Figure 3, where it is assumed that the minimum response will be obtained with placebo (mean change from baseline -4 mmHg) and the maximum response (change from baseline -8 or -9 mmHg) will be reached at the highest dose of ACT-132577 (50 mg).

Figure 3 **Examples of E_{\max} dose-response relationships**

Six candidate dose-response models were pre-specified in the protocol: linear, linear in log-dose, quadratic, E_{\max} , sigmoidal E_{\max} and logistic. The analysis will be performed using the R-package *DoseFinding* [Bornkamp 2016]. A dose-response relationship is demonstrated if at least one of the six MCTs has an adjusted p-value < 0.05. The best fitting model will be selected based on AIC. That model will be used to estimate the minimum effective dose, defined as the dose that achieves a placebo-corrected mean reduction from baseline of at least 4 mmHg with a 95% CI excluding 0.

10.6.4 Supportive/sensitivity analyses

Supportive analyses. The analysis of the primary endpoint in the FAS using LOCF to impute missing Week 8 data will be performed as described in the previous section.

In the PPS as well as the FAS (with LOCF), change from baseline to Week 8 of DB treatment period (Period II) in mean trough SiDBP will be analyzed using an ANCOVA model with a factor for treatment group (placebo and four doses of ACT-132577) and a covariate for baseline mean trough SiDBP. Each of the four doses of ACT-132577 will be compared to placebo applying Dunnett's test. The active comparator will be compared separately versus placebo using an ANCOVA model with a factor for treatment group

(placebo or active comparator) and a covariate for baseline mean trough SiDBP. In the FAS missing data will be imputed by LOCF.

Sensitivity analysis. As a sensitivity analysis for missing data imputation by LOCF an MCP-Mod analysis based on BOCF will be performed in the FAS.

Also in the FAS, changes from baseline to time window Visit 5 (Week 2), time window Visit 4 (Week 4) and Week 8 of DB treatment period (Period II) in mean trough SiDBP will also be analyzed using repeated measurements model. A mixed model will be applied with factors for treatment group, time (Week 2, 4 or 8), treatment by time interaction and a covariate for baseline mean trough SiDBP. An unstructured covariance matrix will be used to account for the correlation between repeated measurements from the same subject. This can be seen as an OC analysis. The treatment group LSMeans obtained from this model will be analyzed using the general MCP-Mod approach [Pinheiro 2014].

Average effect over time. In order to investigate the dose-response on the average treatment effect over time, the same mixed model will be used, but without the treatment by time interaction. Treatment group LSMeans will be analyzed using the general MCP-Mod approach.

10.6.5 Subgroup analyses

Subgroup analyses will be performed on the PPS by age (< 65 versus \geq 65 years), sex, race and country.

In the absence of a published, consolidated approach for subgroup analyses for dose-response, subgroup analyses will be performed by fitting the ‘best’ model from the overall analysis [see Section 10.6.3] in each of the subgroups. The fitted dose-response curves will be compared visually between subgroups. Dose-response by subgroup interaction may be investigated in an ad hoc fashion based on AIC.

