11.3.2.5 Subgroup analyses

Subgroup analyses will be performed by age (\leq 65 versus > 65 years), race and country. This will be done based on the ANCOVA and the repeated measurements model described above. Additional subgroup analyses will be described in the SAP.

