11.5 Sample size

11.5.1 Sample size justification

In a previous study with macitentan in essential hypertension (AC-055-201) the within-group SD for the change from baseline to Week 8 in SiDBP was 7.4 mmHg (90% CI: 7.0–8.0). In the sample size calculations SDs of 7–9 mmHg are considered.

Essential hypertension Protocol AC-080A201 Version 3 30 May 2016, page 91/112

Confidential

It is assumed that the maximum difference versus placebo is achieved at the highest dose of ACT-132577. For the dose-response curves four scenarios were considered [see Figure 2]. These are, in fact, sigmoidal E_{max} curves.

For the sample size it was required that the power to demonstrate the existence of a dose-response relationship is 90% for each of the four scenarios. A total of 70 subjects per group in the PPS (i.e., 420 subjects in total) satisfied this condition and would also allow for sufficiently precise estimation of the dose-response curve. Assuming a drop-out rate of approximately 20%, a total of 90 patients per group would need to be randomized (i.e., 540 in total).

The power for the MCP-Mod approach to demonstrate the existence of a dose-response relationship with 70 subjects per group (PPS) is given in Table 2 for various combinations of placebo-corrected differences and SDs.

Table 2 Power to demonstrate a dose-response relationship with n = 70 per group (PPS)

	Scenario 1	Scenario 2	Scenario 3	Scenario 4
Delta*	4.9	4.5	4.5	4.0
SD				
7	99%	99%	99%	99%
8	99%	99%	99%	99%
9	98%	96%	98%	97%

^{*}Maximum difference versus placebo (mmHg) PPS = Per-Protocol Set

Conservatively assuming that the difference versus placebo is 4 mmHg and the SD is 9 mmHg, the power for the MCP-Mod approach is > 95% for the four scenarios considered.

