11.5.3 Blinded sample size re-estimation

A blinded sample size re-estimation will be performed by the sponsor after 100 subjects have been randomized and their Week 8 BP data are available for analysis (or DB treatment discontinuation before Week 8 is confirmed, where applicable). The sample size recalculation will consider the overall SD of the primary endpoint (change from baseline to Week 8 in mean trough SiDBP, measured by OBPM) in the PPS as well as a more common requirement for the power to detect a dose-response, still allowing for sufficient precision to estimate the dose-response curve [Table 4].

Table 4 Sample size (PPS) needed for 80–95% power to detect a dose-response for various SDs

	SD = 6.0	SD = 6.5	SD = 7.0	SD = 7.5	SD = 8.0	SD = 8.5	SD = 9.0
80% power							
- PPS size	126	150	174	198	222	252	282
- per group*	21	25	29	33	37	42	47
90% power							
- PPS size	174	198	234	264	300	336	378
- per group*	29	33	39	44	50	56	63
95% power							
- PPS size	210	252	288	330	372	420	474
- per group*	35	42	48	55	62	70	79

^{*}Expected number. Power based on the MCT test in the MCP-Mod procedure as implemented in the R *DoseFinding* package, averaged over the four dose-response curves in Figure 2.

Here, SD is the overall standard deviation of the primary endpoint. It is acknowledged that this could be an overestimation of the (unobserved) within group SD, but, given the range of anticipated treatment group differences, this overestimation is likely to be small (< 5%). The recalculated size of the PPS is expected to be between 280 subjects and the originally foreseen 420 subjects.

The number of subjects to be randomized will be calculated by dividing PPS size by the proportion of randomized subjects who were included in the PPS. That proportion will be estimated based on the same 100 randomized subjects considered for the sample size

MCP-Mod = Multiple Comparison procedure - Modeling; MCT = Multiple Contrast Test; PPS = Per-Protocol Set; SD = standard deviation.

Essential hypertension Protocol AC-080A201 Version 3 30 May 2016, page 93/112

Confidential

re-estimation. To be conservative, the lower limit of the 95% CI around the proportion will be employed, of which some examples are given in Table 5.

Table 5 Number and proportion of subjects in PPS and 95% CIs for the proportion at the time of the sample size re-estimation

Number	Number	Proportion	95% CI*	
Randomized	in PPS	in PPS		
100	95	0.95	0.89	0.98
100	90	0.90	0.82	0.95

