8 DEFINITION OF SUBGROUPS

All subgroup analyses will be performed to investigate the consistency of the treatment across subgroups defined by:

Age	< 65 versus \geq 65 years 18–64, 65–84 and \geq 85 years; for European Clinical Trials (EudraCT) Database purposes only
Sex	Female, male
Race	Black or African American; American Indian or Alaska Native; Native Hawaiian or Other Pacific Islander; Asian; White; Other. Categories containing less than 5% of randomized subjects will be considered in the category ‘Other’ for purpose of analysis.
Country	United States (including Puerto Rico, USA); Canada (CAN); Israel (ISR)

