The null hypothesis of ‘no dose-response’ will be rejected if at least one of the six Multiple Contrast Tests (MCTs) has a multiplicity adjusted p-value < 0.05. All statistically significant models (i.e., with an adjusted p-value < 0.05) are fitted in the Mod step and for each model Akaike’s Information Criterion (AIC) is calculated. The smaller the value of AIC (= model deviance + 2 times the number of model parameters), the better the fit. The analysis will be performed using the R-package *DoseFinding* [Bornkamp 2016]. The basic R-code is:

```
library(DoseFinding)
doses <- c(0, 5, 10, 25, 50)
candMod <- Mods(linear = NULL, linlog = NULL, quadratic = -0.005, emax = 50,
               sigEmax = c(50, 0.5), logistic = c(50, 50), doses = doses,
               direction="decreasing")
MMfit <- MCPMod(dose=dose, resp=resp, data=DF, addCovars=~base, models =
candMod, Delta=3)
```

In the Mods function call the candidate models are specified, together with the assumed direction of the effect (decreasing for change from baseline in blood pressure). In the call to the MCPMod function, DF is a data frame with objects dose, resp (for response), and base (for the baseline value) and Delta is a target difference vs placebo (Delta=3 for DBP; Delta=5 for SBP). The object *MMfit* will be summarized to obtain the MCP test, parameter estimates, target dose and AIC. These elements will go in a summary table. The object will be plotted to display the fitted dose-response curves.

Subgroup analyses based on MCP-Mod can be performed by fitting the selected model by subgroup using the *fitMod* function for which the basic R-code is:

```
MMfit1 <- fitMod(dose=dose, resp=resp, data=DF[DF$subg==1,], addCovars=~base,
model=MMfit$selMod)
MMfit2 <- fitMod(dose=dose, resp=resp, data=DF[DF$subg==2,], addCovars=~base,
model=MMfit$selMod)
```

As a supportive analysis to MCP-Mod, change from baseline to Week 8 in DBP and SBP will also be analyzed in an ANCOVA model using the Dunnett test.

```
proc mixed data=dset;
  class treat;
  model outcome=treat base;
  lsmeans treat / adjust=Dunnett diff=control('0') cl;
  where week=8 and treat in (0,1,2,3,4);
run;
```

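### SAP 10.6.5 replaces the protocol's ANCOVA and mixed-model subgroup analyses with separate dose-response fits compared by eye; the change is not declared, and no between-subgroup estimate with an interval is pre-specified.

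*SAP*

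**What the plan says.** Protocol 11.3.2.5 plans subgroup analyses by age, race and country and says of the method: "This will be done based on the ANCOVA and the repeated measurements model described above". It leaves further subgroups to the SAP and names no treatment-by-subgroup term.

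The SAP uses a different method. Section 9.2 says: "Subgroup analyses based on MCP-Mod can be performed by fitting the selected model by subgroup using the" `fitMod` function, and its code fits each subset on its own, so no parameter is shared. Section 10.6.5 applies the best overall model to each subgroup of the PPS (age, sex, race, country), on the ground that no agreed published method exists for dose-response subgroups. The comparison rule is: "The fitted dose-response curves will be compared visually between subgroups". The next sentence permits, without requiring, an AIC-based look at interaction. Table 4 lists only MCP-Mod by subgroup, and 13.6.3 lists MCP-Mod tables and figures by age, sex and race, with no ANCOVA or mixed-model subgroup output.

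On small categories, SAP 8 sets a rule for race only: "Categories containing less than 5% of randomized subjects will be considered in the category" Other. SAP 4.1 declares changes to analysis sets, secondary efficacy analyses and safety analyses, but none to subgroups.

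**The concern.** SAP 8 gives the purpose of these analyses as checking that the treatment is consistent across subgroups. That needs an estimate of how far the subgroups differ and how uncertain the difference is. Separate fits judged by eye do not supply it. An AIC comparison would say which model is preferred, but not by how much the effects differ or with what interval.

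The risk runs both ways: a chance difference in curve shape may be read as real, or a real one dismissed. Protocol 1.3 says the results will be used to select Phase 3 doses, so the curves may be read in that light. A reader comparing the two documents would also not learn from SAP 4.1 that the planned method was dropped.

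**Working it through.** **1. The plan's own figure.** The documents give no power or precision for any subgroup. What can be checked is the whole-trial power in Protocol Table 4, "averaged over the four dose-response curves in Figure 2". Inputs: optimal contrasts for the six candidate models at 0, 5, 10, 25 and 50 mg; equal group sizes; known variance; deltas of 5, 4.5, 4.5 and 4 mmHg from the R program in the sample size re-estimation SAP; and SAP 10.1, "All statistical testing will be performed at a two-sided significance level of 0.05". The Monte Carlo critical value is 2.163. At SD 9 with 47, 63 and 79 per group, average power is 0.812, 0.905 and 0.953, against stated values of 80%, 90% and 95%. The table reproduces, so the same set-up is used below.

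**2. Subgroup sizes.** Shares are not in the documents, so 5% to 30% of the PPS is assumed. With the planned PPS of 420 in six groups (70 per group), a 5% share gives 0.05 × 70 = 3.5 per arm. From the 490 randomized (SAP 4.2) with about 20% lost, it gives 0.05 × 490 × 0.8 / 6 = 3.3.

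**3. Precision.** Protocol 11.5.1: "In the sample size calculations SDs of 7–9 mmHg are considered"; the earlier macitentan study gave 7.4. With n per arm in the smaller subgroup and m = 70 − n in the rest, the 95% half-widths are

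- 50 mg vs placebo within the subgroup: 1.96 × SD × √(2/n)
- difference of that effect between subgroups: 1.96 × SD × √(2/n + 2/m)

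Example at 10% and SD 7.4: 1.96 × 7.4 × √(2/7) = 7.8, and 1.96 × 7.4 × √(2/7 + 2/63) = 8.2. The standard error of the latter is 8.2/1.96 = 4.2, so a true 4 mmHg difference is 4/4.2 = 0.96 standard errors and power is about 16%.

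Each cell gives SD 7.4 / SD 9:

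| Share | n per arm | Half-width, 50 mg vs placebo (mmHg) | Half-width, interaction (mmHg) | Power for a 4 mmHg interaction | Multiple contrast test power inside subgroup |
|---|---|---|---|---|---|
| 5% | 3.5 | 11.0 / 13.3 | 11.2 / 13.7 | 10% / 8% | 16% / 12% |
| 10% | 7 | 7.8 / 9.4 | 8.2 / 9.9 | 16% / 12% | 27% / 20% |
| 20% | 14 | 5.5 / 6.7 | 6.1 / 7.5 | 25% / 18% | 48% / 35% |
| 30% | 21 | 4.5 / 5.4 | 5.3 / 6.5 | 31% / 23% | 64% / 48% |

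The yardstick is SAP 10.6.3: "A placebo-corrected mean reduction from baseline of at least 4 mmHg is considered clinically relevant".

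**4. Stability of the fitted curve.** There were 2,000 simulated least-squares fits per size. The true curve was Emax with ED50 12.5 mg and an effect of 4.5 mmHg at 50 mg; SD was 7.4. Fitting bounds are assumed: ED50 0.05 to 75 mg, Hill exponent 0.5 to 10.

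| n per arm | Emax: ED50 at a bound | Sigmoidal Emax: at a bound | SD of 50 mg effect, Emax fit | SD of 50 mg effect, pairwise difference |
|---|---|---|---|---|
| 70 | 12% | 37% | 1.06 | 1.25 |
| 10.5 | 43% | 69% | 3.03 | 3.23 |
| 7 | 47% | 71% | 3.82 | 3.96 |
| 3.5 | 52% | 76% | 5.61 | 5.59 |

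The last two columns nearly agree. Curve fitting adds instability in shape; it does not make the 50 mg effect noisier.

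**5. AIC as an interaction check.** With k extra parameters and no true interaction, AIC prefers the interaction model when a chi-square on k degrees of freedom exceeds 2k. In large samples that is 16%, 14% and 11% of the time for k = 1, 2 and 3, for each factor examined. The value of k is not given and is assumed.

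**The case against.** The strongest reply is that the primary objective is dose-response, so looking at curves by subgroup fits it; that SAP 10.6.5 gives a reason; and that SAP 10.1 treats everything except the main analysis as exploratory. All of that stands. The stated reason explains adding curves, but not dropping an ANCOVA that SAP 10.6.4 still runs in the whole PPS and FAS.

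Several stronger readings are tempting, and the documents do not support them:

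- **The subgroup fits will be nonlinear and unstable.** Linear, linear-in-log and quadratic models are also candidates and are linear in their parameters. If AIC selects one of them, the ED50 results do not apply.
- **The plan gives no estimate of whether dose-response differs.** Estimates within subgroups are tabulated by age, sex and race, and an AIC check is allowed. What is missing is a pre-specified estimate of the difference with an interval.
- **The curves will be shown without intervals.** The layouts sit in an external standard, so this cannot be told.
- **The age and race subgroups are small.** No shares are given. The figure of about 3.5 per arm is what the 5% rule would permit for a named race category, not a forecast.
- **The SAP removed a protocol interaction test.** The protocol named no interaction term, so adding one goes beyond restoring the protocol.
- **Subgroup consistency is a stated criterion for Phase 3 dose choice.** No section says so.

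**Conclusion.** The point holds as a cheap improvement. The change of method from Protocol 11.3.2.5 is real and is not declared in SAP 4.1, and no between-subgroup estimate with an interval is pre-specified. If an Emax model is chosen, about half of fits at 3.5 to 7 per arm would put ED50 at a bound, against 12% at 70 per arm. This rests on the assumed true curve, SD 7.4 and the assumed fitting bounds.

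ANCOVA would not buy power. In the same subgroups it estimates the 50 mg effect about as imprecisely, and a 50 mg interaction contrast would have about 12% to 31% power for 4 mmHg at assumed shares of 10% to 30%. Its value is that a half-width of roughly 5 to 10 mmHg shows plainly that the data cannot separate the subgroups, which two plotted curves need not show. These half-widths use normal theory without baseline adjustment and are optimistic in the smallest cells. The primary analysis is unaffected.

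**What to change.** In SAP 10.6.5, for each factor, add an ANCOVA of the Week 8 change in SiDBP with treatment, subgroup, treatment by subgroup and baseline. Report:

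- placebo-corrected differences with 95% CI for each dose in each subgroup;
- one treatment-by-subgroup contrast named in advance, for example 50 mg vs placebo, with 95% CI and labelled descriptive. For race and country, name the reference category beforehand.

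Keep the fitted curves as a supplement with confidence bands. Add the new outputs to Table 4 and 13.6.3, and declare the departure from Protocol 11.3.2.5 in SAP 4.1, including the dropped repeated-measurements subgroup analysis if it is not restored.

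Forcing a common ED50 across subgroups is not recommended as a rule. It would steady the curves but could hide a difference in potency; Protocol 1.2.1 reports 1.2- to 1.3-fold higher exposure in elderly subjects.

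The cost is SAP wording, one standard model per factor, and a few more exploratory tables whose interaction contrasts have low power and should be described that way.
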